## Statistical Analysis Plan

Patients will be divided into control or intervention with center randomisation. Full Analysis Set (FAS): Analyzes all cases that were randomized into clinical trials. The shed data was estimated using the LOCF method. Per Protocol Set(PPS): Analysis of all cases that meet the test plan, good compliance, no banned drug use during the trial, and complete the contents of the CRF regulations. The efficacy analysis of this trial was simultaneously analyzed using the full analysis set and the compliance set. The entire analysis will be undertaken with “the intention-to-treat” principle, even though we have foreseen a “by protocol” analysis. only patients who have received at least the minimum established doses of PEA treatment in the experimental arm will be evaluated.

The descriptive analysis will be performed using means and SDs for quantitative variables and absolute and relative frequencies for qualitative variables. To verify the homogeneity of both groups,  $\chi^2$  (Pearson or Fisher) and t-test will be used. To determine the benefit of our intervention, the clinical relevance indicators will be calculated: relative risk, absolute risk reduction, relative risk reduction, number needed to treat.

Specific analysis method:

1. Statistical descriptions were performed for the cases of rejection and shedding and for pretreatment data, Pearson  $\chi^2$  test was used for all-cause mortality within 28 and 90 days.
  2. Pearson  $\chi^2$  test or exact probability calculation, t-test or analysis of variance and non-parametric test were performed for other outcomes.
  3. the central effect CMH method was performed for the comparison of the clinical efficacy of the two groups, and the qualitative or ordinal variables are analyzed by using the GEE method.
  4. A statistical description method was used for adverse reactions. Chi-square or Fisher exact test were used for the incidence of adverse reactions between groups.
  5. Survival analysis: Cox survival curve; multivariate analysis: unconditional logistic regression;
- All analyses will be performed with a significance of 5% and the associated CI of each relevant parameter will be calculated. The statistical software used will be IBM SPSS Statistics V.22.

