Variables and measurements

The primary outcome is all-cause mortality assessed at 28 days from the recruitment of the patient.

Moreover, at the descriptive level and in order to check the homogeneity of both groups, the following variables will be collected at the time of recruitment: birth year, gender, height, dry weight, body temperature, heart rate, blood pressure, count blood cell, glucose level, plasma creatinine, bilirubinaemia, plasma C reactive protein, procalcitonin level, blood gas analysis, lactate, urinary output(mL/kg/hours), arterial oxygen tension/fractional inspired oxygen ratio, International Normalized Ratio(INR),Prothrombin time(second),activated partial thromboplastin time(second),Fibrinogen(g/L),D-Dimer(mg/L),Organ function(Acute Physiology and Chronic Health Evaluation II, Sequential Organ Failure Assessment, The Confusion Assessment Method for The Intensive Care Unit).

Secondary Outcome: all-cause mortality within 90 days from randomization ,free hours of vasoactive drugs after randomization within 14 days.

Finally, for all patients enrolled in the study, 10 ml of whole blood was taken from 8 am to 10 am every day, After centrifugation, the plasma was stored in a negative 80-degree refrigerator for subsequent follow-up testing.

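### LOCF is the only missing-data rule for the full analysis set and mortality is not exempted, so read literally a patient of unknown vital status at day 28 or 90 counts as a survivor

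*SAP*

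**What the plan says.** The SAP's opening paragraph defines the full analysis set (FAS): "Analyzes all cases that were randomized into clinical trials". The next sentence is the only missing-data rule in either document: "The shed data was estimated using the LOCF method". It names no endpoint, and shedding is not defined.

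The protocol (Variables and measurements) states: "The primary outcome is all-cause mortality assessed at 28 days from the recruitment of the patient". The secondary outcomes are "all-cause mortality within 90 days from randomization ,free hours of vasoactive drugs after randomization within 14 days". Under Specific analysis method, item 1, the SAP says that a Pearson chi-square "test was used for all-cause mortality within 28 and 90 days". It also plans "relative risk, absolute risk reduction, relative risk reduction, number needed to treat".

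Three other lines touch on dropouts:

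- Item 1 describes them: "Statistical descriptions were performed for the cases of rejection and shedding".
- The per-protocol set (PPS) requires "good compliance, no banned drug use during the trial, and complete the contents of the CRF regulations".
- Item 5 names a Cox survival curve, with no endpoint and no censoring rule.

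The protocol's sample-size paragraph (under Setting and design) adds 10% for shedding. Neither document describes how vital status is to be ascertained in patients who leave the study.

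**The concern.** Death is an absorbing state. If vital status at day 28 is unknown, the last observed status was alive, and carrying it forward asserts that the patient survived to day 28. This has two consequences.

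- Mortality in an arm is understated by the fraction lost times the risk of death among the lost.
- If that product differs between arms, the absolute risk reduction (ARR) is biased, in whichever direction the difference runs. The trial is open-label, so equal loss cannot be presumed.

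The rule reaches the primary endpoint. The other planned analyses do not repair the FAS result. Describing dropouts changes no estimate. The PPS also selects on compliance and banned drugs, so it is a different comparison. The Cox analysis stands beside the chi-square test and does not replace it.

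**Working it through.** **Inputs.** From the protocol's sample-size paragraph: control mortality 0.40, odds ratio 0.36, 76 per arm, 10% allowance, total 168. The test is taken as Pearson at two-sided 5%, which matches the 0.0250 target alpha in the protocol's table. All loss rates and their split by arm are assumptions.

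**The plan's own figures.** The treated odds are 0.36 × 0.40/0.60 = 0.24, so P1 = 0.24/1.24 = 0.1935. Exact binomial enumeration at 76 per arm gives power 0.8041, as in the table. 152 × 1.10 = 167.2, rounded up to 168, or 84 per arm. With 84 per arm and no loss, power is 84.6%.

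**Effect of LOCF.** Let p be true mortality in an arm, m the fraction with unknown status and k the risk of death among them. LOCF analyses p − m·k. Complete cases analyse (p − m·k)/(1 − m). The result depends on k, so two settings were used, both with no true effect (p = 0.40 in each arm).

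- *Setting A: the lost carry the full 28-day risk* (in effect, lost at day 0). Here k = 0.40.
- *Setting B: constant hazard, with loss spread evenly over 28 days and independent of death.* The chance of being alive when lost is 0.40/(−ln 0.60) = 0.40/0.5108 = 0.783. Then k = (0.783 − 0.60)/0.783 = 0.234.

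At 15% loss on PEAF and 5% on control:

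| | Setting A | Setting B |
|---|---|---|
| LOCF mortality, PEAF v control | 34.0% v 38.0% | 36.5% v 38.8% |
| LOCF false findings for PEAF (nominal 2.5%) | 7.7% | 4.9% |
| LOCF two-sided error (nominal 5%) | 8.3% | 6.0% |
| Complete-case mortality | 40.0% v 40.0% | 42.9% v 40.9% |
| Complete-case two-sided error | 4.9% | 5.7% |

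For example, in setting B on PEAF, LOCF gives 0.40 − 0.15 × 0.234 = 0.365 and complete cases give 0.365/0.85 = 0.429. Complete cases are then biased against PEAF, with 4.4% false findings for control, because early deaths are kept while patients lost alive are dropped.

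**Smaller losses, no true effect.**

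- At 5%/1%, LOCF false findings for PEAF are 4.0% in setting A (two-sided error 5.4%) and 3.3% in setting B.
- At 2%/1% in setting A they are 2.8%, against 2.7% for complete cases.

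**Planned effect, setting A.**

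- Equal 10% loss: the relative risk stays at 0.48. The ARR falls from 20.6 to 0.90 × 20.6 = 18.6 points and the NNT rises from 4.8 to 5.4. Power is 78.9%, against 80.4% for complete cases. With 40% mortality in both arms, two-sided error stays at about 5%.
- Loss of 5% on PEAF and 15% on control: the ARR is 0.40 × 0.85 − 0.1935 × 0.95 = 0.156. Power is 64.2%, against 79.4% for complete cases.

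**The case against.** **The rule may not be meant for mortality.** It is one generic sentence, and the protocol has a non-mortality outcome, vasoactive-free hours. That is possible, but the SAP does not say so and offers no other rule for unknown vital status.

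**Few patients may be affected.** The patients are in intensive care and have blood taken daily, so much early status may be seen directly. Shedding may include patients who left the protocol but whose vital status is known. This stands as a limit on the size. It does not settle status at day 28 or day 90, because the documents do not say how long patients are observed.

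**The larger figures depend on an assumption about timing.** This stands. Setting A gives the lost the whole 28-day risk. A patient lost later has already survived part of it, and setting B shows a smaller effect. Two-sided error under LOCF is also clearly inflated only at the widest imbalance examined (15%/5%). The shift toward one arm is more visible than the total error.

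**Complete cases are not a clean benchmark.** This stands too. They are unbiased in setting A and biased the other way in setting B.

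A reader might infer that the plan inflates the benefit of PEAF, or that about 10% of patients will be misclassified. The documents support neither. The 10% is a planning allowance for an undefined category, with no split by arm. Heavier loss on control would work against PEAF.

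**Conclusion.** The gap in the wording is certain: the only stated rule, applied as written, turns unknown vital status into survival in the primary test. The direction and size of any bias are not known. They depend on how many patients have unknown status, how they split between arms, when they were lost and their risk of death.

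Under the assumptions examined, the effect runs from negligible at 1-2% loss to roughly two or three times the nominal rate of false findings for PEAF at 15%/5% loss (4.9% to 7.7% against 2.5%). Neither figure is a bound, because loss that depends on prognosis could do more. With equal loss unrelated to outcome, the relative risk and type I error hold and only the ARR and power slip. This should be fixed before analysis, but it is not evidence that the trial's result would be wrong.

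**What to change.** 1. State that LOCF is not used for 28- or 90-day mortality.
2. Define shedding so that stopping treatment or leaving the protocol is not treated as a missing outcome.
3. Ascertain vital status at days 28 and 90 for every randomised patient, and record the date of last contact. The protocol's list of variables does not include that date.
4. For any status still unknown, prespecify one primary method that uses the time already survived. Options are Kaplan-Meier 28- and 90-day risks censored at last contact, with the Cox analysis censored the same way, or imputation conditional on survival to last contact. Do not make complete cases the primary method.
5. Report the number with unknown status by arm, with best- and worst-case bounds as a sensitivity analysis.

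The cost is SAP wording, a vital-status check, one extra date and a little more analysis. No patients are added. Confidence intervals widen slightly. As a rough guide, take 15 and 30 known deaths with 8 lost per arm. The 95% half-width for the ARR is 13.1 points under LOCF (84 per arm) and 14.2 points if the lost are left out (76 per arm). No method removes bias from loss that depends on unmeasured risk of death, so step 3 matters most.

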According to the mortality rate of patients with sepsis combined with MODS in our hospital for about one year is about 40%. The literature reported that the OR of coupled plasma-filtration adsorption(CPFA)treatment group was 0.36 (according to $\alpha=0.05$, unilateral, $1-\beta=0.8$; $n=152(76\times 2)$), according to statistical principles, The sample size calculated by PASS11.0 requires at least 152 cases, an increase of 10% of shedding cases. the total number of cases is at least 168 subjects finally.

	Sample Size Grp 1	Sample Size Grp 2	Prop H1 Grp 1 or Trtmnt P1	Prop Grp 2 or Control P2	O.R. if H0 OR0	O.R. if H1 OR1	Target Alpha	Actual Alpha	Beta
Power	N1	N2	P1	P2	OR0	OR1	Alpha	Alpha	Beta
0.8041	76	76	0.1935	0.4000	1.000	0.360	0.0250	0.0259	0.1959

Methods:

The patients are considered registered once the informed consent form has been obtained by the patient or legal representative. The recruitment process ends with the patient center randomisation. Patients will be divided randomly into two arms (control and intervention).

The characteristics of the groups are: Control group: Treatment following the suggestions provided by the recent surviving sepsis guidelines, as well as standard care guidelines typically followed in China. HVHF, High volume hemofiltration for septic shock with MODS is permitted in Control group routinely (Blood pump: 200ml/min, replacement fluid pump 45ml/kg/min, dialysate pump 45ml/kg/min, waste pump 90ml/kg/min, and high-volume hemofiltration for 16 hours with ACF180™ AsahiKASEI or AV1000S™ Fresenius)

Intervention group: the patient is placed in the PEAF group, he/she will receive treatment with PEAF immediately after randomization. PEAF that is TPE (therapeutic plasma exchange 20ml/kg/d Fresh frozen plasma, Blood pump: 120ml/min, replacement pump 20ml/kg/min, dialysate pump 0ml/kg/min, waste pump 20ml/kg/min, plasma exchange 1 hour) plus PFA (Blood pump: 120ml/min, Plasma separation rate 25-30%, plasma-filtration adsorption with Mediasorb™ BELLECO ITALY

≥30ml/min) and HVPDF(High volume plasma diafiltration with ACF180™ AsahiKASEI or Ultraflux AV1000S™ Fresenius , Blood pump same as PFA , replacement fluid pump 2000ml/h, dialysate pump 2000ml/h, waste pump 4000ml/h),with PFA and HVPDF for 15 hours in the first 3 days. Same protocol with control group after 3days.

The scheme of the trial is displayed in figure 1 and figure 2

[figure not shown]

Figure 1: Study diagram

[figure not shown]

Figure 2: Pipeline connection

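### The SAP gives conflicting rules on which patients decide efficacy: both analysis sets at once, intention-to-treat throughout, and a minimum-dose limit in the experimental arm tied to no set

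*SAP*

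**What the plan says.** All the relevant text is in the SAP. The analysis-sets paragraph contains five statements that bear on who is counted:

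- FAS: "Full Analysis Set (FAS): Analyzes all cases that were randomized into clinical trials".
- PPS: "Analysis of all cases that meet the test plan, good compliance, no banned drug use during the trial, and complete the contents of the CRF", among the requirements.
- Role in efficacy: "The efficacy analysis of this trial was simultaneously analyzed using the full analysis set and the compliance set".
- Governing principle: "The entire analysis will be undertaken with “the intention-to-treat” principle, even though we have foreseen a “by protocol” analysis".
- Dose restriction: "only patients who have received at least the minimum established doses of PEA treatment in the experimental arm will be evaluated".

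The closing bullet of the SAP adds "All analyses will be performed with a significance of 5" per cent, with no distinction between sets. No set is called primary, supportive or sensitivity. No rule covers the case where the two sets disagree. The dose restriction names no set, and the text of neither document gives the minimum it refers to.

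The primary outcome is 28-day all-cause mortality (Protocol, Variables and measurements). It is compared by a Pearson chi-square test (SAP, Specific analysis method, item 1).

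**The concern.** The three sentences on efficacy cannot all be followed literally. An analysis done entirely by intention-to-treat does not give a compliance-selected set the same role. A rule that evaluates only adequately dosed experimental patients does not include everyone randomised.

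This matters because the trial is open, and the PPS is defined by what happens after randomisation. PEAF is given over the first 3 days (Protocol, Methods), in patients whose expected mortality is about 40%. A PEAF patient who dies early may fall short of the minimum dose and drop out of the PPS. No matching dose condition removes a control patient. If the FAS gave p = 0.08 and the PPS p = 0.03, the SAP would lean towards reporting no demonstrated benefit, but no sentence in it would stop the PPS result from being presented as the efficacy finding.

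**Working it through.** **1. The plan's own figure.** The inputs are in Protocol, Setting and design: control mortality 0.40, OR 0.36, power 0.80.

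- Treated risk: odds 0.36 × 0.40/0.60 = 0.24, so p1 = 0.24/1.24 = 0.1935, as tabulated.
- n per arm = [z(α)·√(2·p̄·(1−p̄)) + z(β)·√(p1(1−p1) + p2(1−p2))]² / (p2−p1)², with p̄ = 0.2968.
- With z(α) = 1.960 and z(β) = 0.842: (1.266 + 0.530)² / 0.2065² = 75.6, so 76 per arm. Exact enumeration gives power 0.8041, matching the table.
- One-sided 0.05 gives only 60 per arm. The sample size therefore rests on 0.025 one-sided (0.05 two-sided), as in the table's target alpha, although the text above it says 0.05 one-sided. The SAP does not state sidedness.
- 152 × 1.10 = 167.2, rounded up to 168, or 84 per arm.

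The documents give no error rate for using the two sets together, so the rest is computed under stated assumptions.

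**2. Either set may win, exclusions unrelated to outcome.** Let d be the share of patients excluded from the PPS (assumed). The two test statistics then correlate at about √(1−d). For two tests each at two-sided 5%:

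- two-sided error = 1 − P(|Z1| < 1.96 and |Z2| < 1.96)
- false PEAF benefit = 1 − P(Z1 < 1.96 and Z2 < 1.96), with Z oriented so that large values favour PEAF

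| d | correlation | two-sided error | false PEAF benefit |
|---|---|---|---|
| FAS alone | – | 5.0% | 2.5% |
| 10% | 0.949 | 6.5% | 3.2% |
| 20% | 0.894 | 7.1% | 3.5% |
| 30% | 0.837 | 7.6% | 3.8% |

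A simulation of 1,000,000 null trials (84 per arm, 40% mortality in both arms, Pearson test) gives 6.5%, 7.1% and 7.6% two-sided, and 3.2%, 3.5% and 3.8% for false benefit. The value for independent tests, 1 − 0.95² = 9.75%, does not apply because the sets overlap heavily. If the tests were one-sided at 5%, false benefit would be 6.3%, 6.9% and 7.3% against 5%.

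**3. Exclusions related to outcome.** Assume no treatment effect, and that early deaths equal to 5% or 10% of the PEAF arm leave the PPS while no control patient does. Expected deaths per arm are 0.40 × 84 = 33.6.

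| Early PEAF deaths removed | share of that arm's deaths | PEAF mortality in PPS | control mortality | false PEAF benefit |
|---|---|---|---|---|
| 5% of arm (4.2) | 12.5% | 29.4/79.8 = 36.8% | 40% | 6.1% |
| 10% of arm (8.4) | 25% | 25.2/75.6 = 33.3% | 40% | 13.8% |

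The last column is simulated as in step 2, with success in favour of PEAF on either set. The PPS alone gives the same 6.1% and 13.8%, so testing two sets contributes nothing here: this is selection bias in the PPS. Two-sided either-set error in these scenarios is 8.6% and 16.3%.

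**4. FAS alone decides.** Simulated two-sided error is 4.9% and false PEAF benefit 2.5%, whatever happens in the PPS.

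**The case against.** The best defence is the intention-to-treat sentence. It covers the entire analysis, follows directly after the statement about both sets, and mentions the by-protocol analysis only as a concession. With the FAS defined as all randomised cases, the natural reading is that the FAS leads. That stands, and it limits the point. It does not close it: the sentence does not withdraw the equal role just given to the PPS, does not call the by-protocol analysis supportive, and is followed by a restriction that pulls the other way.

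A reader might infer two stronger things, and the documents support neither.

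- *That a PEAF benefit may be claimed on whichever set is significant, so the false-positive risk exceeds 5%.* The SAP states no such rule; analysing two sets side by side is not a success criterion. The 5% line is generic and also covers baseline and adverse-reaction tests, so it gives the PPS no confirmatory standing. Even under an either-set rule, the figures above 5% in step 2 are two-sided and include false harm. False benefit from two-sided 5% tests stays below 5% when exclusions are unrelated to outcome.
- *That the dose restriction governs every analysis and abandons intention-to-treat.* It comes straight after the mention of the by-protocol analysis and probably continues it. The defect is that the SAP does not say so.

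It is also fair to object that the 6% and 14% rest on assumed, one-arm loss of deaths. The PPS requirement of a completed CRF could remove early deaths from the control arm as well, which would reduce the imbalance.

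**Conclusion.** The point holds as a conflict in the SAP's wording on which patients decide efficacy. The text leans to the FAS but never says that it decides, and it leaves an experimental-arm dose restriction attached to no set.

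The multiplicity cost is modest and conditional. If either set could carry the claim, and 10% to 30% of patients were excluded regardless of outcome, two-sided error would be about 6.5% to 7.6%, and false PEAF benefit about 3.2% to 3.8% against 2.5%. The selection cost is larger: about 6% or 14% false benefit if early deaths equal to 5% or 10% of the PEAF arm left the PPS. All of these assume 84 per arm, 40% mortality in both arms, two-sided 5% tests and exclusion rates that the documents do not supply. They show what an unclear rule could allow and do not predict this trial's error rate. Because the clarification bears on the primary mortality claim and costs almost nothing, it should be made before the data are analysed.

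**What to change.** Replace the sentence on simultaneous analysis, and tie the dose restriction to one set, with wording such as:

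*The 28-day mortality comparison is decided on the FAS alone (all randomised patients, analysed as allocated). The PPS is a supportive sensitivity analysis, reported with its estimate and confidence interval, and cannot by itself support an efficacy claim. The minimum-dose condition in the experimental arm applies only to the PPS.*

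The last sentence is needed. Without it, the dose restriction would still contradict a decision based on all randomised patients.

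The cost is a few lines of SAP text, with no new patients, data or analyses. The sponsor gives up one option: claiming efficacy from the PPS when the FAS is not significant.

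### The by-protocol rule requires a minimum amount of treatment in the PEAF arm only, so PEAF patients who die before reaching it are excluded because of the outcome

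*SAP*

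**What the plan says.** The analysis-sets paragraph of the SAP defines two sets. The full analysis set (FAS) "Analyzes all cases that were randomized into clinical trials". The per-protocol set (PPS) takes cases that "meet the test plan, good compliance, no banned drug use during the trial, and complete the contents of the CRF regulations"; these criteria name no arm and so apply to both. On their roles the SAP says "The efficacy analysis of this trial was simultaneously analyzed using the full analysis set and the compliance set", and then "The entire analysis will be undertaken with “the intention-to-treat” principle, even though we have foreseen a “by protocol” analysis". The next sentence reads "only patients who have received at least the minimum established doses of PEA treatment in the experimental arm will be evaluated".

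The Protocol (Methods, Intervention group) says that on allocation to PEAF "he/she will receive treatment with PEAF immediately after randomization", and describes the course as "with PFA and HVPDF for 15 hours in the first 3 days. Same protocol with control group after 3days". In the control group, high-volume hemofiltration is allowed as routine, but no minimum amount is set. Under Variables and measurements, "The primary outcome is all-cause mortality assessed at 28 days from the recruitment of the patient".

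Neither document states what the minimum is, gives a treatment minimum for controls, or says how a death before the minimum is classified.

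**The concern.** On the natural reading, the last SAP sentence defines the by-protocol analysis announced just before it. Eligibility for that analysis then depends on something that happens after randomisation, in one arm only, during a period in which the primary event can occur. A PEAF patient who dies before the minimum leaves both the numerator and the denominator of PEAF mortality. A control who dies on the same day meets no such threshold. The two groups are no longer selected in the same way.

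At stake is how the per-protocol result is read. It is to be produced alongside the FAS result, and the SAP does not say that it is only supportive or what happens if the two disagree. A skewed per-protocol result could be taken as independent confirmation. The trial is open-label and the minimum is not stated, so the threshold could also be settled after outcomes are known.

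**Working it through.** The plan gives no figure for this point, so there is none to reproduce. The check asks what the filter does when PEAF has no effect.

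**Inputs from the documents.** 168 patients in two equal arms, so 168/2 = 84 per arm; 40% mortality (both from the sample size paragraph of the Protocol); Pearson χ² test at 5% (SAP).

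**Assumptions.** True 28-day mortality is 40% in both arms. The documents give none of the following:

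- f = share of the PEAF arm excluded as early deaths
- s = share of the PEAF arm excluded as under-treated survivors
- g = share of controls dropped as early deaths under the general PPS criteria

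**Formulas.**

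- PEAF mortality after exclusion = (0.40 − f)/(1 − f − s), with 84(1 − f − s) patients, rounded
- Control mortality after exclusion = (0.40 − g)/(1 − g), with 84(1 − g) patients, rounded
- False benefit (or false harm) = probability that the uncorrected Pearson test is significant with PEAF mortality lower (or higher), by exact binomial enumeration

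With no exclusions, each probability is 2.48%.

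Worked example, f = s = 5%, g = 0: (0.40 − 0.05)/(1 − 0.10) = 0.35/0.90 = 38.9%, 76 PEAF patients against 84 controls at 40%; false benefit 3.5%.

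| Case | Exclusions | f = 2% | 5% | 10% | 15% |
|---|---|---|---|---|---|
| 1 | s = f, g = 0: PEAF mortality (control 40%) | 39.6% | 38.9% | 37.5% | 35.7% |
| 1 | false benefit | 2.9% | 3.5% | 5.0% | 7.4% |
| 2 | s = f, g = f/2: false benefit | 2.4% | 2.2% | 2.1% | 2.2% |
| 3 | s = f, g = f: false benefit | 2.0% | 1.3% | 0.6% | 0.3% |
| 3 | false harm | 3.5% | 4.3% | 7.6% | 11.8% |
| 4 | s = g = 0 (upper end): false benefit | 3.5% | 6.1% | 13.9% | 28.2% |

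**Where the bias changes sign.** With g = 0, setting (0.40 − f)/(1 − f − s) = 0.40 gives 0.60f = 0.40s, so s = 1.5f. Beyond 1.5 excluded survivors per excluded death, the filter works against PEAF:

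- f = 2%, s = 5%: PEAF mortality 0.38/0.93 = 40.9%, false benefit 2.0%, false harm 3.6%
- f = 5%, s = 10%: PEAF mortality 0.35/0.85 = 41.2%, false benefit 1.8%, false harm 3.6%

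With g = f/2, the break-even ratio falls to between 0.77 and 0.92 survivors per death, so case 2 roughly cancels.

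The last entry of case 4 needs 0.15/0.40 = 37.5% of all PEAF deaths to come before the minimum, with no under-treated survivors excluded and no early control deaths dropped. It is an outer bound, not an expectation.

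**The case against.** The strongest reply is that the governing analysis is untouched. The SAP puts the whole analysis under intention-to-treat and includes every randomised case in the FAS. That stands, and it limits the point to the per-protocol comparison.

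Second, the direction is not fixed. PEAF starts at once, so a low minimum would exclude few deaths, while a high one would also exclude survivors who stopped early. If an early death counts as poor compliance or an incomplete CRF, the general PPS criteria already remove early deaths from both arms. The one-arm sentence then adds only under-treated PEAF survivors, and the bias runs against PEAF (case 3). This also stands. It means the size and sign depend on unwritten rules; it does not make the comparison fair.

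Third, only one arm receives the device, so a dose condition naming only that arm is not in itself an error. That is correct. The fault is that the condition does not protect a patient who dies while being treated as assigned, and that no adherence rule of comparable kind is stated for controls.

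Fourth, the sentence stands apart from the PPS definition, so applying it to the by-protocol analysis is an inference. It is the natural one. Applied to the whole analysis, the sentence would contradict the FAS definition.

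**Conclusion.** The concern holds. As written, the rule filters one arm after randomisation on a condition that death can prevent, and the resulting per-protocol mortality comparison is not like with like. The FAS result is unaffected on the ordinary reading.

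Confidence is high for the asymmetry and moderate for the direction. The likely direction favours PEAF, because death directly stops a patient reaching the minimum, but the documents do not settle it. Across the assumed scenarios, the nominal 2.5% false-benefit rate ranges from 0.3% to 7.4% when survivors are excluded as often as deaths, and reaches 28.2% only at the outer bound; false harm reaches 11.8% when early control deaths are dropped equally often. All these figures rest on assumed exclusion shares, 84 per arm and 40% true mortality in both arms. This should be fixed, but as a repair to a secondary analysis.

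**What to change.** Three changes to the SAP:

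1. State that the FAS, analysed as randomised, decides 28-day mortality, and that the PPS is supportive.
2. Delete the one-arm sentence. Alternatively, assign it explicitly to the PPS and replace it with an adherence rule stated for both arms, under which a patient treated as assigned until death is kept. If a minimum is retained, state it in advance and judge it only against treatment due while the patient was alive. Because hemofiltration is optional in controls, their side of the rule can be worded as managed as assigned rather than as an amount of treatment.
3. State that early death counts neither as poor compliance nor as an incomplete CRF.

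The cost is SAP wording only; no dose or treatment schedule changes. The downside is that the PPS will keep some patients with little PEAF exposure, and its result may look less favourable to PEAF.
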